8.3 REPORTING PROCEDURES

8.3.1 ADVERSE EVENT REPORTING

Any adverse device effect discovered during the study should be recorded on the Adverse Event CRF by an investigator and reported to MED-EL. Investigators are responsible for determining if the adverse event meets the definitions for device -related, serious, and/or unanticipated. Questions regarding classification should be directed to the MED-EL Clinical Monitor. All ADEs should be reported to the MED-EL Clinical Monitor in a timely manner. All adverse device effects will be reported to the FDA and to relevant IRBs in the annual report. Investigators should reference the flow chart below (Figure 1) and Section 8.3.2 to determine appropriate reporting procedures, depending on AE type.

(FIGURE 2)

8.3.2 UNANTICIPATED SERIOUS ADVERSE DEVICE EFFECT REPORTING

If the investigator determines that the adverse event is unanticipated, serious, and device-related, the CRF should be submitted to the MED-EL Study Monitor no later than 10 working days after becoming aware of the event. Additionally, the investigator should notify the reviewing IRB of the unanticipated serious adverse device effect within 10 working days.

Upon receiving this documentation, MED-EL will review and submit the information to FDA within 10 working days. Additional reports concerning the effect will be submitted upon FDA request.

8.4 STUDY HALTING RULES

MED-EL will review all serious, unanticipated adverse device effects to determine if the study should continue per the protocol, be modified, or be discontinued. Examples of findings that would trigger a safety review are the number of serious adverse events occurring overall, the number of occurrences of a particular type of serious adverse event, or increased frequency of events (e.g., device deficiencies). If findings indicate that the study or protocol should be reconsidered, MED-EL will inform FDA of the disposition of the study.

A stopping rule of three unanticipated serious adverse device effects would prompt suspension of enrollment and/or study intervention use. Based on the definitions of an Adverse Device Effect, Serious Adverse Event, and Unanticipated Adverse Event provided in Sections 8.1.2, 8.1.3, and 8.1.4, respectively, a Serious unanticipated Serious Adverse Device Effect:

1. Results in death, injury, or illness that is life-threatening; results in permanent impairment or damage to the body; or requires medical or surgical intervention to prevent death, life-threatening injury/illness, or permanent harm to the body,
2. Is unanticipated in nature, severity, or frequency from the known potential risks,
3. Is related or possibly related to participation in the research,
4. Suggests that the research places participants or others at a greater risk of harm than was previously known or recognized, and
5. There is a reasonable possibility that the device caused the event

9 CLINICAL MONITORING

Clinical monitoring is conducted to ensure that the rights and well-being of subjects are protected, that study data are accurate, complete, and verifiable, and that the study is being conducted in compliance with the approved protocol/amendment(s), with GCP, and with applicable regulatory requirements. MED-EL Corporation personnel and/or a qualified Contract Research Organization (CRO) will be responsible for monitoring this investigation according to MED-EL Corporation's SOPs.

Clinical monitors will conduct on-site pre-study site visits at each prospective site. During this visit, the monitor will evaluate the facilities and staff and review study-specific details and obligations with investigators. Investigators will demonstrate understanding of the following information at the conclusion of the pre-study site visit:

- Obligation to conduct the study in accordance with the investigator agreement, GCP, and other applicable regulations
- Device accountability and traceability requirements for investigational devices
- Requirements for a well-controlled study
- Investigator's role in the process of obtaining parental permission
- Obligation to obtain and maintain IRB approval
- Importance of complete and accurate study records, including source documentation
- Required monitoring and clinical monitor access to the study records
- Time commitments for investigators involved in the study
- Details specific to the investigational plan

Once the study and enrollment have begun, periodic monitoring will occur. The type and frequency of these visits will depend on the number of subjects enrolled, the completion or accuracy of study records received by MED-EL, and the occurrence of adverse events and protocol deviations. These periodic site visits will evaluate whether:

- The facilities continue to be acceptable for the study
- The protocol is being followed
- Changes to the protocol have been reported to and approved by the IRB
- Verification of source documentation and source data
- Reports to the Sponsor and IRB are accurate, complete, and on time

After completion of any monitoring visit, the clinical monitor will document the observations, conclusions, and corrective actions taken to address any findings. The documentation will include the visit date, name of the monitor, name of the investigator and site, and address of the site. Case report forms and other related study documentation will be reviewed as MED-EL receives the completed paperwork throughout the study. Completed study records will be reviewed 100% for missing data entries. Accuracy of study records will be monitored based on the investigator's history, accuracy of study records, the rate of adverse events, and the occurrence of protocol deviations.

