4 STUDY DESIGN

4.1 OVERALL STUDY DESIGN

This prospective, single-site IDE study uses an open-label, single-arm, repeated-measures design with participants serving as their own control. One US academic medical center will enroll 20 experienced MED-EL CI users to evaluate the design and usability of the SONNET 3 (EAS) Audio Processor (AP). Participants may enroll before or at Visit 1. Each participant will complete a 3-week trial with the SONNET 3 (EAS) AP. Participants will return 2-4 weeks after Visit 1 to complete a custom survey comparing AP design (Visit 2). Study objectives will assess patient-reported improvement in AP design and compare usability with the SONNET 3 (EAS) AP to participants' existing SONNET (EAS) or SONNET 2 (EAS) AP. The primary endpoint will demonstrate superiority of the SONNET 3 (EAS) AP design compared to the existing AP designs.

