6.1.2 DETAILS OF MANUFACTURER

The SONNET 3 (EAS) Audio Processor is manufactured by MED-EL Elektromedizinische Geräte GmbH. MED-EL Corporation is the US importer and the sponsor of this clinical trial.

[figure not shown]

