7.1.2 STUDY INTERVALS

- Visit 1: Enrollment/Baseline
- Visit 2: 3-week Interval (2-4 weeks after Visit 1)
- Enrollment Conclusion

Testing can occur outside of the provided window with prior approval from MED-EL.

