10.3 ANALYSIS DATASETS

The intent-to-treat (ITT) population is defined as all enrolled participants including withdrawn participants who have been replaced. The modified ITT (mITT) population is defined as all participants who completed Visit 1 and Visit 2. The per protocol (PP) population is defined as participants who:

- Completed Visit 1 and Visit 2
- Were using the SONNET 3 (EAS) device consistently throughout the trial period
- Are free from major protocol deviations, including but not limited to:
 - Non-use of the SONNET 3 (EAS) during the trial
 - Missing test measures from one or more intervals
 - Evidence of not meeting inclusion/exclusion criteria after completion of study intervals

Analysis for the primary endpoint will be completed on the mITT and the PP populations.

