10.4.7 PLANNED INTERIM ANALYSES

No interim analysis will be conducted for this study.

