12 QUALITY ASSURANCE AND QUALITY CONTROL

MED-EL will implement all necessary procedures to ensure the integrity of CRFs. As part of the periodic monitoring visits, the clinical monitor will compare all study records to the source documents and ADD-source data to verify accuracy. When CRFs are received, the forms will be reviewed for completeness and to identify any inconsistencies or errors. Investigators will be trained to make corrections only by approved methods. Any discrepancies found in the CRFs by the Clinical Monitor should be brought to the attention of the investigator.

For the data management process, data may be entered into a database using accepted data entry techniques. Database validation will be performed after the last study interval has been completed. A more comprehensive evaluation of the database will be performed as required i.e., data analysis.

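### Per-protocol membership is left to judgement, with no named decision-maker and no sign-off before scores are seen, in an open-label study whose records the sponsor reads as they arrive; neither mITT nor PP is named as primary

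*Combined protocol and SAP*

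**What the plan says.** All references are to the combined protocol and SAP.

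- **Who sees the records, and when.** Section 9: "Case report forms and other related study documentation will be reviewed as MED-EL receives the completed paperwork throughout the study". Section 12 adds: "When CRFs are received, the forms will be reviewed for completeness and to identify any inconsistencies or errors". Section 6.1.2 identifies the reviewer: "MED-EL Corporation is the US importer and the sponsor of this clinical trial". Section 9 allows a CRO to monitor as well as, or instead of, sponsor staff. Under Section 14.3 the sponsor also receives the deviation log.
- **What the records show.** Section 4.1: "This prospective, single-site IDE study uses an open-label, single-arm, repeated-measures design". Under Section 10.4.2 a participant is a success if the mean of the Design answers exceeds 3, and the proportion of successes is compared with 77%.
- **How PP is defined.** Section 10.3 requires completion of both visits and two further conditions: "Were using the SONNET 3 (EAS) device consistently throughout the trial period", with no threshold, and "Are free from major protocol deviations, including but not limited to", which introduces an open list. One listed item is evidence, found after the study intervals, that eligibility was not met. Section 5.2 includes an exclusion for unrealistic motivation or expectations, which is itself a judgement.
- **How mITT is defined.** Everyone who completed Visits 1 and 2.
- **What is tested.** Section 10.3 runs the primary analysis on mITT and PP and ranks neither. Section 10.4.1 sets the level at 0.05.
- **What protects the decisions.** Section 10.4.7: "No interim analysis will be conducted for this study". Section 10.5 lists only the paired design as a measure against bias. Section 12 places database validation after the last interval but says nothing about fixing the analysis sets before scores are seen.

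**The concern.** In a blinded trial, exclusions made during data review are protected because the reviewer does not know the treatment. Here there is nothing to unblind. One short survey gives each participant's outcome, and the people who handle deviations may already have read it. A judgement on whether someone used the device consistently, or whether an unlisted deviation is major, can then be made knowing whether that person helps or hurts the result. No intent is needed: a low rating can itself prompt a closer look at that participant's adherence.

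With 20 participants, one exclusion can move the PP result across the significance line. mITT and PP could then disagree, and the plan does not say which one answers the primary question.

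**Working it through.** **Inputs.** Null share 0.77, one-sided, level 0.05, n = 20, effect size h = 0.36 and stated power 85% (Section 10.2). Success is a Design mean above 3 (Section 10.4.2). The documents do not name the test used for the analysis, so an exact binomial test is assumed.

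**The plan's own figure.** One-sample arcsine power is Φ(h√n − 1.645) = Φ(0.36 × √20 − 1.645) = Φ(1.610 − 1.645) = Φ(−0.035) = 0.486, so the stated 85% is not reproduced. That is a separate matter and does not decide this point. What is used here is the true share that h implies: sin²(asin√0.77 + 0.18) = 0.901, rounded to 90% below.

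**Step 1: all 20 analysed.** P(X ≥ r | n, 0.77) is the sum over x from r to n of C(n,x) 0.77^x 0.23^(n−x).
- P(X = 20) = 0.0054, P(X = 19) = 0.0321, P(X = 18) = 0.0910.
- 19/20: p = 0.0054 + 0.0321 = 0.037, passes.
- 18/20: p = 0.037 + 0.091 = 0.128, fails.

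**Step 2: one low rater excluded from PP.** With n = 19, P(X = 19) = 0.0070 and P(X = 18) = 0.0396, so 18/19 gives p = 0.0465 and passes. mITT stays at 18/20 and still fails.

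**Step 3: does this depend on the exact test?** Normal approximation, z = (p̂ − 0.77)/√(0.77 × 0.23/n):
- 18/20: z = 0.13/0.0941 = 1.38, p = 0.084, fails.
- 18/19: z = 0.1774/0.0965 = 1.84, p = 0.033, passes.

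If success were read simply as an observed share of at least 77%, the pivot moves but remains: 15/20 = 75.0% fails and 15/19 = 78.9% passes.

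**Step 4: how often would one exclusion be decisive?** At an assumed true share of 90%, P(exactly 2 low of 20) = 190 × 0.10² × 0.90¹⁸ = 190 × 0.01 × 0.1501 = 0.285.

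**Step 5: worst case for type I error.** At a true share of 0.77, suppose one low rater can be set aside after scores are seen whenever that helps. PP then passes with 19 or 20 successes, or with 18 successes and one exclusion. The PP type I error becomes P(X ≥ 18 | 20, 0.77) = 0.128, against 0.037 when membership is settled without sight of the scores.

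**The case against.** The strongest reply is that this is ordinary monitoring. The stated purpose of the review is to find missing entries, inconsistencies and errors. No running tally is described, and the sentence in Section 9 does not name the APCS. A low rater who completed both visits cannot leave mITT, so a favourable PP exclusion would produce a visible split. On this view, tighter PP definitions and a named primary population would remove most of the exposure without restricting monitors.

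Most of this stands. That survey scores reach the sponsor during enrolment is an inference, though a reasonable one: the APCS is completed at Visit 2, and the review extends beyond CRFs to related study documentation. What does not follow is that nothing is needed. The deviation list is open-ended, so better definitions still leave some calls to judgement, and a split result is no safeguard while the plan does not say which population prevails.

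A reader might go further than the documents allow, in four ways:

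- **That the sponsor decides who counts.** No section says so. PP classification and replacement are assigned to nobody, and Section 5.4.1 gives termination to the site principal investigator. The one such power given to the sponsor by name is in Section 7.1.2: "Testing can occur outside of the provided window with prior approval from MED-EL". That approval comes before the participant's own survey.
- **That replacement can remove a known low rater.** Section 5.4.2 covers people who do not complete all intervals. The APCS is given only at Visit 2, so they would normally have no Design score.
- **That reading forms amounts to an interim analysis and contradicts Section 10.4.7.** No interim test, stopping rule for effectiveness or change of sample size is planned, and looking without acting does not alter type I error.
- **That early visibility of failure measures harm.** At a 90% true share, two or more low ratings have appeared by the 15th participant in 1 − 0.9¹⁵ − 15 × 0.1 × 0.9¹⁴ = 45% of trials, but no decision in the plan depends on that.

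**Conclusion.** The point holds in a limited form. The plan allows, and does not guard against, PP decisions made with sight of the participant's own Design result, and it leaves open which population carries the primary conclusion. mITT itself is not exposed.

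One PP exclusion turns 18/20 (p = 0.128) into 18/19 (p = 0.0465). Exactly two low ratings, the situation in which this matters, occur in 28.5% of trials at an assumed true share of 90%. The rise in PP type I error from 0.037 to 0.128 is an upper bound: it assumes selective removal of one low rater whenever that helps, and it is not a prediction of conduct. The p-values and error rates assume an exact one-sided test. The one-exclusion reversal also appears under the normal approximation.

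**What to change.** 1. **Section 10.3, primary population.** Name mITT as the population that carries the primary conclusion, with PP supportive. This alone removes most of the exposure.
2. **Section 10.3, PP membership.** Name who classifies deviations. Require that classification and PP membership be decided participant by participant by someone without access to that participant's Design scores, and be signed and dated before any Design scores are tabulated or released for analysis.
3. **Sections 9 and 12, access.** Until that sign-off, those who classify deviations see only whether the APCS has been completed. Monitors who do not classify deviations may still verify survey data against source. A complete bar on monitor access is not needed: it would delay source verification, and the site would still hold the scores.

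Cost: one sign-off step and a limited access restriction. No extra participants or visits are needed.

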10 STATISTICAL CONSIDERATIONS

10.1 STATISTICAL HYPOTHESES

Primary Endpoint:

At least 77% of participants will report improvement (mean score >3 on a 6-point Likert scale) in processor design with the SONNET 3 (EAS) compared to the existing audio processor on the Design subsection of the Audio Processor Comparison Survey (APCS) at Visit 2.

Secondary Endpoints:

1. Summary of patient-reported satisfaction rating (6-point Likert scale) on subsections of the Audio Processor Comparison Survey (APCS) with SONNET 3 (EAS) at Visit 2.
2. Summary of audiologist-reported satisfaction ratings on subsections of the Audiologist Survey at enrollment conclusion.

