3 OBJECTIVES AND ENDPOINTS

OBJECTIVES	ENDPOINTS	JUSTIFICATION FOR ENDPOINTS
Primary		
To demonstrate patient-reported improvement in processor design with the SONNET 3 (EAS) (EAS) Audio Processor (AP) compared to the existing AP.	At least 77% of participants will report improvement in processor design with SONNET 3 (EAS) (EAS) compared to the existing AP on the Design subsection of the Audio Processor Comparison Survey (APCS) at Visit 2.	Based on changes in size, weight, and earhook, we expect the majority of users to report improved design with SONNET 3 (EAS). Warren et al., 2019 ¹ compared useability of a novel AP to the existing design and found that, 77% of participants reported improvement in design. A mean score >3 (6-point Likert scale) on the APCS Design subsection will indicate agreement with improved design of SONNET 3 (EAS).
Secondary		
	Summary of patient-reported satisfaction ratings (6-point Likert scale) on subsections of the APCS with SONNET 3 (EAS) (EAS) at Visit 2.	The APCS includes the Bluetooth Pairing, Backwards Compatibility, and Parent Impressions subsections to assess different areas of SONNET 3 (EAS) (EAS) usability.
	Summary of audiologist-reported satisfaction ratings on subsections of the Audiologist Survey at enrollment conclusion.	The Audiologist Survey assesses the clinician perspective on usability improvements with SONNET 3 (EAS) (EAS).

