10.2 SAMPLE SIZE

The sample size estimate is based on attaining adequate power to test the primary hypothesis that at least 77% of participants will report subjective improvement in audio processor design with SONNET 3 (EAS) over the existing processor based on a single survey. The hypothesis test is a one-sample, one-sided test of the proportion of participants reporting an average score of >3 on the Audio Processor Comparison Survey (APCS) compared to 77%, based on the clinical trial for the Cochlear Nucleus 7 audio processor, where an average of 77% of participants responded with greater than neutral agreement (>50 on a 100-point scale) on survey questions addressing satisfaction with improved comfort with the new audio processor. For the purpose of this sample size calculation, 77% will represent the desired participant response proportion.

A power analysis was conducted using a binomial two-proportion test with the package 'pwr' in R. Using a 95% confidence interval, a sample size of 20 participants would provide 85% probability of rejecting the null hypothesis (H_0 : 77%). Calculations are based on the following assumptions:

- Hypothesized proportion: H_0 : $p < 0.77$;
- Expected proportion: H_1 : $p \geq 0.77$
- Significance level = 0.05
- One-sided
- Effect size $h=0.36$

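### The primary endpoint as worded is met at 16/20, the plan's one-sided 0.05 test needs 19/20, Section 10.4.2 does not say which decides, and the stated 85% power is about 40%

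*Combined protocol and SAP*

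**What the plan says.** The endpoint sentence appears in the synopsis (Section 1.1), in Section 3 and in Section 10.1. Section 10.1 has "At least 77% of participants will report improvement (mean score >3 on a 6-point Likert scale) in processor design", and Section 3 has "At least 77% of participants will report improvement in processor design with SONNET 3 (EAS) (EAS) compared to the existing AP". Section 4.1 attaches a claim to it: "The primary endpoint will demonstrate superiority of the SONNET 3 (EAS) AP design compared to the existing AP designs".

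Section 10.2 treats the same statement as a hypothesis. The sample size is chosen "to test the primary hypothesis that at least 77% of participants will report subjective improvement in audio processor design", and "The hypothesis test is a one-sample, one-sided test of the proportion of participants reporting an average score of >3", with 77% as the comparator. It gives H0: p < 0.77, H1: p ≥ 0.77, a one-sided 0.05 level and h = 0.36, and concludes that "a sample size of 20 participants would provide 85% probability of rejecting the null hypothesis". It also describes the power method as a two-proportion test and refers to a 95% confidence interval without giving its sidedness. Section 10.4.1 repeats the 0.05 level.

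Section 10.4.2, the primary analysis section, averages each participant's Design items, sets the share averaging above 3 against 77%, and restates H0 and H1. It names no test, p-value, confidence bound or required count, and does not say that the endpoint is met only if H0 is rejected.

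Section 10.3 adds: "Analysis for the primary endpoint will be completed on the mITT and the PP populations". It does not say which of the two sets decides success.

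**The concern.** An observed share of at least 77% and a rejection of 77% at one-sided 0.05 are different conditions, and with 20 participants they are three improvers apart. The analysis section is where a reader would look to see which one governs. It leaves the matter open, and its H1 (p ≥ 0.77) has the same form as the endpoint sentence, so an observed 80% can be presented as agreeing with H1.

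At stake is the study's only confirmatory result. With 16 or 17 improvers, the endpoint could be reported as met, and the Section 4.1 superiority claim made, although the plan's own test does not reject. The study is open-label and single-arm, so a success rule fixed before the data are seen is one of its few safeguards. A reader of Section 10.2 would also believe that the test has 85% power.

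**Working it through.** **Inputs.** n = 20, null share 0.77, one-sided 0.05, h = 0.36 and stated power 85% (all Section 10.2); 0.05 level (Section 10.4.1). I assume that all 20 are analysed.

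**1. The plan's power figure.** The arcsine (Cohen h) formulas give:
- One-sample: Φ(h√n − 1.645) = Φ(0.36 × √20 − 1.645) = Φ(−0.035) = 48.6%.
- Two-sample, 20 per group: Φ(h√(n/2) − 1.645) = Φ(0.36 × √10 − 1.645) = Φ(−0.507) = 30.6%.
- Two-sided versions: 36.3% and 20.6%.

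None gives 85%. By the one-sample formula, 85% needs n = ((1.645 + 1.036)/0.36)² = 55.5, so 56, or h of about 0.60 at n = 20.

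**2. The endpoint sentence as a count.** 15/20 = 75% falls short and 16/20 = 80% meets it.

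**3. The test as a count.** One-sided p-values against 0.77:
- Exact: P(X ≥ r) for X ~ Binomial(20, 0.77).
- Score: z = (r/20 − 0.77)/√(0.77 × 0.23/20).
- Wald: z = (r/20 − 0.77)/√((r/20)(1 − r/20)/20).
- Arcsine: z = (2 asin√(r/20) − 2 asin√0.77) × √20.

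| Improvers | Exact | Score | Arcsine | Wald |
|---|---|---|---|---|
| 16/20 | 0.499 | 0.375 | 0.372 | 0.369 |
| 17/20 | 0.292 | 0.198 | 0.180 | 0.158 |
| 18/20 | 0.128 | 0.084 | 0.055 | 0.026 |
| 19/20 | 0.037 | 0.028 | 0.007 | 0.0001 |

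The pass mark is 19/20 for exact, score and arcsine, and 18/20 for Wald.

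**4. Properties of each pass mark.** h = 0.36 above 0.77 corresponds to p = 0.901.

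| Pass mark | Type I error at p = 0.77 | Power at p = 0.901 |
|---|---|---|
| 16/20 (endpoint sentence) | 49.9% | 95.8% |
| 18/20 (Wald) | 12.8% | 68.2% |
| 19/20 (exact, score, arcsine) | 3.7% | 39.7% |

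**5. How often the sentence and the test disagree.** P(16 or 17) = P(X ≥ 16) − P(X ≥ 18):
- p = 0.77: 0.4986 − 0.1284 = 0.370.
- p = 0.90: 0.9568 − 0.6769 = 0.280.

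The count of 18 is a further disagreement unless Wald is used.

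**6. The confidence-interval wording.** At 19/20 the one-sided 95% Clopper-Pearson lower bound is 0.784, above 0.77. The two-sided 95% lower limit is 0.751, below 0.77; at 20/20 it is 0.832. A two-sided interval would therefore need 20/20.

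**The case against.** The strongest reply is that the plan already specifies its test. Section 10.2 gives a one-sample, one-sided test and equates power with rejecting H0, Section 10.4.1 sets 0.05, and Section 10.4.2 lists the hypotheses. Together these make a one-sided 0.05 test the natural reading, and 16/20 counts as success only if two of those sections are set aside. This stands, and it limits the severity. It does not remove the conflict, because three sections still state the endpoint as an observed share and none ties success to rejection.

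A second reply is that the unnamed test hardly matters at n = 20. That is largely right: exact, score and arcsine agree on 19/20, and nothing in the documents suggests Wald.

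Third, the boundary point in H1 is said to be cosmetic. Moving it indeed leaves the pass mark unchanged; the only gain is that H1 stops echoing the endpoint sentence.

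Two stronger readings are tempting. A reader might infer that 16 to 18 improvers is the likeliest range at the planned effect. It is not: at p = 0.90 that range has probability 56.5%, against 74.5% for 17 to 19. A reader might also infer that the choice between exact and score tests will decide the result once fewer than 20 are analysed. The per-protocol set does require that participants "Were using the SONNET 3 (EAS) device consistently throughout the trial period", so it may be smaller. But Section 5.4.2 allows replacement of participants who do not complete all study intervals, and no figure in the documents predicts 17 or 18 analysed.

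**Conclusion.** The point holds as an unresolved conflict between the endpoint sentence and the planned test, together with a power figure that is wrong as written. With 20 analysed, the sentence is met at 16 and the test rejects at 19 (18 under Wald). At 16 or 17 the two disagree under every test considered, with probability 37% at p = 0.77 and 28% at p = 0.90.

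A reader might infer that the trial runs a confirmatory test with a type I error near 50%. The documents do not support that: 49.9% would apply only if the endpoint sentence were used as the pass mark, and it is not the error rate of the planned test.

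The success-rule wording is a should-fix. The power statement should be corrected in any case: at h = 0.36 and n = 20 it is about 40% exact, or 48.6% by the one-sample arcsine formula, against the stated 85%. All counts assume that 20 participants are analysed.

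**What to change.** **Section 10.4.2.** State H0: p ≤ 0.77 versus H1: p > 0.77, tested by an exact one-sided binomial test at 0.05, with the endpoint met only if H0 is rejected. Give the pass mark as 19/20 if 20 are analysed, recomputed for the actual number. Say which of mITT and PP decides success.

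**Sections 1.1, 3 and 10.1.** Align the endpoint sentence with that rule.

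**Section 10.2.** Replace the reference to a 95% confidence interval with the one-sided 0.05 test. Restate the power at p about 0.90 and n = 20 as about 40% (exact).

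**Alternative.** Call 77% a descriptive target, and drop the 0.05 test and the Section 4.1 superiority claim.

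**Cost.** These are wording changes only, with no new data and no added participants. The downside is an explicit, stricter pass mark and a less favourable stated power. More participants would be needed only if the sponsor wished to keep 85% power at p = 0.90 with the exact test: about 60, with a pass mark of 52/60 (type I error 4.6%, power 85.8%).
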